# Intensity (Severity)

Mild	An AE is mild if the subject is aware of but can easily tolerate the sign or symptom.
Moderate	An AE is moderate if the sign or symptom results in discomfort significant enough to cause interference with the subject's usual activities.
Severe	An AE is severe if the sign or symptom is incapacitating and results in the subject's inability to work or engage in their usual activities.

For every AE in the study, the Investigator must assess the causality (Related or Not Related to the medical device or study procedure). An assessment of causality will also be performed by Study Sponsor utilizing the same definitions, as shown below:

# Causality

Related	An AE classified as related may be either definitely related or possibly related		
	where a direct cause and effect relationship with the medical device or study		
	procedure has not been demonstrated, but there is a reasonable possibility that		
	the AE was caused by the medical device or study procedure.		
Not Related	An AE classified as not related may either be definitely unrelated or simply		
	unlikely to be related (ie, there are other more likely causes for the AE).		

The Study Sponsor will assess the AEs and may upgrade the Investigator's assessment of seriousness and/or causality. The Study Sponsor will notify the Investigator of any AEs that is upgraded from non-serious to serious or from unrelated to related.

# 11.4 Return product analysis

Study Sponsor representatives and their contact information are provided in the Manual of Procedures that accompanies this protocol.

Alcon products associated with device deficiencies and/or product related AEs should be returned and must include the Complaint # which will be provided by Study Sponsor after the

Page 58 of 70

case is entered in the Study Sponsor's Global Product Complaint Management System (GPCMS).

# **11.5 Unmasking of the Study Treatment**

Not applicable; this study is open-label.

# **11.6 Follow-Up of Subjects with Adverse Events**

The Investigator is responsible for adequate and safe medical care of subjects during the study and for ensuring that appropriate medical care and relevant follow-up procedures are maintained after the study.

The Investigator should provide the Study Sponsor with any new safety information (which includes new AEs and changes to previously reported AEs) that may affect the safety evaluation of the device. For AEs that are unresolved/ongoing at time of subject exit from study, any additional information received at follow-up should be documented in the eCRFs up to study completion (ie, database lock).

All complaints received after this time period will be considered and processed as spontaneous (following the post-market vigilance procedures) and should be communicated to the medical device's manufacturer as per local requirements.

The Investigator should also report complaints on non-Alcon products directly to the manufacturer as per the manufacturer's instructions or local regulatory requirements

# **11.7 Pregnancy in the Clinical Study**

Women of childbearing potential are not excluded from participation. If a woman becomes pregnant during the study, the pregnancy is not reportable as an AE; however, complications may be reportable and will be decided on a case–by-case basis. An Alcon form will be utilized to capture all pregnancy-related information until birth of the child.

# **12 ANALYSIS PLAN**

# **12.1 Subject Evaluability**

The final subject evaluability will be determined using the Deviations and Evaluability Plan (DEP) prior to locking the database.

# 12.2 Analysis Sets

There will be two effectiveness analysis sets. The All Implanted Analysis Set (AAS) includes all eyes with successful IOL implantation, T3-T6 and recommended by ORA. The Per Protocol Analysis Set (PPS) includes all eyes with successful IOL implantation, T3-T6 and recommended by ORA and with no major protocol deviations. The primary analysis set for effectiveness is the PPS.

Safety Analysis Set (SS) will include all eyes with attempted implantation with any IOL (successful or aborted after contact with the eye) and will be used for the safety analyses.

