Subject population	Subjects who require cataract surgery and a Toric IOL in both eyes. Subjects will be required to have preoperative keratometric astigmatism of 0.75 D to 3.00 D and require the AcrySof IQ ® Toric SN6AT3 – 6 as determined by Alcon Toric Calculator.
Key inclusion criteria (See Section 8.1 for a complete list of inclusion criteria)	
 
Inclusion Criteria:
 
1. 22 years of age or older
 
2. Preoperative keratometric astigmatism of 0.75 to 3.00 D
 
3. Planned implantation of AcrySof IQ Toric SN6AT3 – T6 as determined by the Alcon Toric Calculator
 
4. Potential postoperative visual acuity of 0.04 logMAR (20/20) or better
 

**Document:** TDOC-0055329 **Status:** Effective

	5. Willing and able to complete all required postoperative
	visits
	6. Able to comprehend and sign the informed consent form
Key exclusion	Exclusion Criteria:
criteria	
(See Section 8.2 for a	1. Unclear intraocular media other than cataract
complete list of	2. Axial length $< 21.5$ and $> 27.0$ mm
avaluaion aritaria)	3. Significant irregular corneal astigmatism as measured by a
exclusion cinterna)	1 Unstable tear film per Investigator judgement
	5 Significant anterior or posterior segment disease
	6. Prior intraocular or corneal surgery
	7. Prior retinal detachment
	8. Pregnancy or lactation, current or planned, during the course of the study
	
 
9. Participation in another concurrent clinical trial per the PI indgement
 

	
 
10. Presence or history of any condition or finding that makes the subject unsuitable as a candidate for cataract surgery or study participation or may confound the outcome of the study, in the opinion of the Investigator.
 

	Exclusion Criteria During Surgery
	
 
Intra-op complications such as but not limited to posterior capsular tear, wound burn and need to place a suture
 
ORA or Alcon Toric Calculator recommends an IOL other than AcrySof IQ Toric SN6AT3-T6
 

Data analysis and	No formal statistical hypothesis testing is planned in support of the
sample size	primary objective Rather the data will be summarized using
justification	descriptive statistics by treatment group.
	There will be two effectiveness analysis sets. The All Implanted
	Analysis Set (AAS) includes all eyes with successful IOL
	implantation, T3-T6 and recommended by ORA. The Per Protocol
	Analysis Set (PPS) includes all eyes with successful IOL

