	implantation, T3-T6 and recommended by ORA and with no major
	protocol deviations. The primary analysis set for effectiveness is the PPS.

	• $20/32$ Snellen or better: $\leq 0.24 \log MAR$
	• 20/40 Snellen or better: $\leq 0.34 \log MAR$
	In addition, descriptive statistics including sample size, mean, median, standard deviation, number of subjects/eyes, minimum, maximum and (two-sided) 95% confidence interval will be presented.
	Descriptive statistics for adverse events (including SSIs) will be presented for study eyes. The rates of all adverse events will be provided with counts and percentages, and these rates will be accompanied by two-sided exact 95% confidence intervals.
	In order to estimate the percent of eyes with BCDVA of 20/20 or better (ie, $\leq 0.04 \log$ MAR) at 6 months postop, the 95% confidence interval for the percent of eyes with BCDVA of 20/20 or better at 6 months postop will be calculated based on the binomial distribution. With a sample size of 90 eyes, per the binomial distribution, the width of the 95% confidence interval ranges from 4.0% to 21.5%. As an example, for an observed outcome of 70%, the 95% confidence interval per binomial distribution is (59.4%, 79.2%) with a width of 19.8%.
Key words	ORA, Verifeye+, Barrett, Toric, IOL

Alco Docu Statu	n - B ment: s: Effec	usiness Use Only Proto TDOC-0055329 tive	col - Cl Versi	inical	.0; Most	-Recent	; Effec	tive; CU	JRRENT	Eff	ective D	22
		Early Exit		x	x						$\mathbf{X}^{+}$	_
		Visit 5A Day 120 – 180 days Post Visit 00A		x	x						$\mathbf{X}^{+}$	
	Both eyes	Visit 4A Day 80 – 100 days Post Visit 00A		x	x						$\mathbf{X}^{+}$	_
		Visit 00Å										

Printed By:

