# 7 INVESTIGATIONAL PLAN

## **Study Design** 7.1

This is a prospective, randomized, contralateral, multicenter, postmarket study. A total of 115 subjects will be enrolled to achieve 90 evaluable subjects. Treatments will be randomized between eyes and the eye with more visually significant cataract as measured by BCDVA will undergo surgery first. If the BCDVA is equal between eyes, the right eye will undergo surgery first.

The Barrett Toric Calculator via the Alcon Toric Calculator will be used for IOL power selection preoperatively. Sites that have LenSx will use it for primary and secondary incisions, capsulorhexis, and phacofragmentation consistently in both eyes for all subjects. Sites that don't have LenSx will use standard manual procedures.

For the eyes in the ORA with VerifEye + study group, the IOL power and axis and axis mark alignment will be provided by ORA. For eyes in the Barrett Toric study group, the IOL power and axis will be provided by the Barrett Toric Calculator and axis alignment will be done manually (ie, without ORA guidance).

The study will be conducted at up to 10 sites in the US. Surgery will be done on each eye on different days 7 to 14 days apart. Total follow-up duration is 6 months. There will be 10 visits in total. Refer to the Overview of Study Procedures Table for an overview of the visit schedule and the assessments to be performed at each visit.

## Page 38 of 70

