# 9.3 Treatment Assignment / Randomization

Subjects will be randomized in a 1:1 ratio to receive treatment with ORA System with VerifEye+ or the Barrett Toric Calculator in the first treated eye, respectively. Since this is a contralateral study, each subject should have one eye treated with each technique.

Only after signing the ICF, a subject will be assigned a subject number by the electronic data capture system.

A randomization list will be generated using a validated system that automates the random assignment of treatment arms to randomization numbers in the specified ratio. Subjects will be assigned to treatment according to the randomization list uploaded in the IRT system. The randomization list will be generated and maintained by the Study Sponsor.

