1.2 Study Description

This is a prospective, randomized, contralateral, multicenter, postmarket study. A total of 115 subjects will be enrolled to achieve 90 evaluable subjects. Treatments will be randomized between eyes and the eye with more visually significant cataract as measured by BCDVA will undergo surgery first. If the BCDVA is equal between eyes, the right eye will undergo surgery first.

The IOL power will be determined using any IOL power calculator. Sites that have LenSx will use it for primary and secondary incisions, capsulorhexis, and phacofragmentation consistently in both eyes for all subjects. Sites that don't have LenSx will use standard manual procedures.

For the eyes in the ORA with VerifEye + study group, the IOL toric power and axis and axis mark alignment will be provided by ORA. For eyes in the Barrett Toric study group, the IOL toric selection and axis will be provided by the Barrett Toric Calculator and axis alignment will be done manually (ie, without ORA guidance).

The study will be conducted at up to 10 sites in the US. Surgery will be done on each eye on different days 7 to 14 days apart. Total follow-up duration is 6 months. There will be 10 visits in total. The study flow chart is available in Figure 7-1 of the protocol, and schedule of study procedures and assessments are available in Table 3-1 of the protocol.

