2.1 Effectiveness Analysis Sets

There will be two effectiveness analysis sets. The All implanted set (AAS) includes all eyes with successful IOL implantation, T3-T6 and recommended by ORA. The Per Protocol Analysis Set (PPS) includes all eyes with successful IOL implantation, T3-T6 and recommended by ORA and with no major protocol deviations. The primary analysis set for effectiveness is the PPS.

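### The AAS and the primary PPS require an ORA-recommended lens for all eyes, with no counterpart for the eyes randomized to the Barrett Toric Calculator

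*Protocol*

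**What the plan says.** Protocol 12.2 defines the first effectiveness set: "The All Implanted Analysis Set (AAS) includes all eyes with successful IOL implantation, T3-T6 and recommended by ORA". The PPS uses the same condition and adds the absence of major protocol deviations. The section then states: "The primary analysis set for effectiveness is the PPS".

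SAP 2.1 repeats the rule: "The All implanted set (AAS) includes all eyes with successful IOL implantation, T3-T6 and recommended by ORA". The protocol summary has it for the AAS ("implantation, T3-T6 and recommended by ORA. The Per Protocol") and for the PPS ("implantation, T3-T6 and recommended by ORA and with no major"). No arm qualifier appears in any of these places.

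The design is contralateral: "each subject should have one eye treated with each technique" (Protocol 9.3). On where the Barrett eye's lens comes from, Protocol 7.1 says: "For eyes in the Barrett Toric study group, the IOL power and axis will be provided by the Barrett Toric Calculator". SAP 1.2 says that "the IOL toric selection and axis will be provided by the Barrett Toric Calculator".

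The primary objective and endpoint (Protocol 12.4.1) cover lenses selected by either method, and Protocol 12.4.1.2 reports results by treatment group.

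**The concern.** The primary set is defined by a recommendation from one of the two methods under study, and that definition is applied to the eyes of both. For an ORA eye the condition has a plain meaning. For a Barrett eye it has none that the documents state.

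That Barrett eyes belong in the set is clear from the objective and the by-group reporting. Which Barrett eyes belong is not clear. The answer fixes the denominator of the Barrett percentage and its confidence interval, and these are the result of a descriptive study. Site and sponsor are unmasked (Protocol 9.4), and SAP 4.6 plans an interim database lock and summary at 1 month. If the rule stays open, it may be settled by whoever programs the sets, with outcomes already visible. SAP section 3 also uses the AAS, alongside the safety set, for the by-treatment baseline and conduct tables.

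**Working it through.** **1. The passages side by side**

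| Item | ORA eyes | Barrett eyes |
|---|---|---|
| Source of lens selection (Protocol 7.1, SAP 1.2) | ORA | Barrett Toric Calculator |
| ORA-recommended power listed for recording (Protocol 10.3.2) | Yes | Not listed |
| Implanted power listed for recording (Protocol 10.3.2) | Yes | Yes |
| ORA recommendation required for AAS and PPS (Protocol 12.2, SAP 2.1) | Yes | Yes, as written |

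The ORA measurement row in the schedule of procedures is marked at both surgery visits with no split by arm. It does not show that Barrett eyes are measured: the ORA eye may be operated first or second, so both visits need the mark in any case. It does not exclude it either.

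**2. What the rule does as written**

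- If Barrett eyes have no ORA recommendation, none meets the condition, and the Barrett percentage has no denominator.
- If ORA was captured in Barrett eyes, only those whose lens ORA also recommended stay. This conditions Barrett eyes, after randomization, on agreement with the other device. ORA eyes face no such cross-check during surgery.

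**3. Readings that would keep all Barrett eyes, none of them stated**

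- The condition applies to ORA eyes only.
- It is the ORA side of exclusion 12 (Protocol 8.2), which concerns the T3-T6 range and names both methods, with inclusion 5 (Protocol 8.1) covering the Alcon Toric Calculator side at entry. It would then add little to the T3-T6 condition already in the sentence.

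**4. The plan's own precision figures**

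Protocol 12.8 and SAP section 8 use the binomial distribution. With x successes in n eyes, the exact (Clopper-Pearson) 95% limits are

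lower = Beta(0.025; x, n − x + 1), upper = Beta(0.975; x + 1, n − x).

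For n = 90:

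- 63/90 (70%): 59.4% to 79.2%, width 19.8 points, as in Table 12-1.
- 72/90 (80%): 70.2% to 87.7%, width 17.4 points, as in Table 12-1.
- Narrowest width 4.0 points (0/90 or 90/90) and widest 21.5 points (45/90), as stated.

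The sample-size arithmetic is sound.

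**5. Illustration for the cross-agreement reading**

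The documents give no rate at which ORA and the Barrett calculator recommend the same lens. Assume 100% and 50%, applied to 90 Barrett eyes, with 80% observed:

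| Assumed agreement | Barrett eyes | Successes | Exact 95% CI | Width (points) |
|---|---|---|---|---|
| 100% | 90 × 1.00 = 90 | 72 | 70.2% to 87.7% | 17.4 |
| 50% | 90 × 0.50 = 45 | 36 | 65.4% to 90.4% | 25.0 |

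The base of 90 is itself uncertain. It is the planned number of evaluable subjects out of 115 enrolled, and if evaluable already means inclusion in the analysis set, the filter would be counted twice.

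**The case against.** The strongest reply is that the intent is obvious. The objective names both methods, results are given by group, and inclusion 5 and exclusion 12 already tie every eye to T3-T6, so no statistician would drop the Barrett arm. This stands as far as it goes: Barrett eyes are meant to be included. It does not say which ones, and the readings above keep different eyes.

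A reader might infer more: that the text itself removes every Barrett eye, and so half of the planned eyes. The documents do not support that. It needs the further premise that no Barrett eye has an ORA recommendation matching its lens, and no passage says so. Protocol 7.1 bars ORA guidance in Barrett eyes for axis alignment only, the schedule row has no arm split, and parts of the public text are redacted. The absence of an item from the Barrett procedure list is silence, not proof.

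It may also be said that the Deviations and Evaluability Plan (Protocol 12.1) will settle the matter before database lock. That plan is not among the documents. It might clarify the rule, but nothing shown says that it changes the set definitions.

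Finally, the consequence is limited. No hypothesis test is planned (Protocol 12.4.1.1), the SAP executive summary gives no success criterion, and the safety set does not carry the condition. All of this stands. It bounds the damage to the effectiveness estimates and to the AAS tables.

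**Conclusion.** The definition is wrong as written, not merely short of detail. In all three places the primary set depends on an ORA recommendation for every eye, and for Barrett eyes this either fails or acts as a one-sided filter after randomization. It should be corrected before database lock.

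The size is conditional. If no Barrett eye has an ORA recommendation, the Barrett percentage cannot be estimated under the literal rule. If ORA was captured in Barrett eyes, the loss depends on an agreement rate that is not given; the widening from 17.4 to 25.0 points rests on an assumed 50% agreement, an observed 80% and a base of 90 eyes. If the condition was meant for ORA eyes only, or as the range rule only, all Barrett eyes can stay. The size and direction of any bias cannot be computed from the documents.

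**What to change.** In the protocol summary, Protocol 12.2 and SAP 2.1, replace the ORA condition with: *recommended by the method to which the eye was randomized (ORA or Barrett Toric Calculator)*, applied the same way in both arms. If only the range rule of exclusion 12 was meant, say that instead and name both methods.

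State which component of the lens must match the recommendation. This first requires Protocol 7.1 and SAP 1.2 to be reconciled: the former has the Barrett Toric Calculator supply the IOL power in Barrett eyes, while the latter allows any power calculator and leaves the toric selection and axis to Barrett.

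The cost is a wording amendment to both documents before database lock, with IRB/IEC approval under Protocol section 4 unless the change counts as administrative. The sponsor should also confirm that the eCRF captures the Barrett-recommended lens and the toric model. The Protocol 10.3.2 lists name lens powers but neither of these items, so it cannot be assumed that the data for the corrected rule are already recorded.

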# 12.3 Demographic and Baseline Characteristics

Summary statistics will be provided for demographic and baseline characteristics by treatment group. Number and percentage will be presented for categorical variables and descriptive statistics including mean, standard deviation (SD), minimum, and maximum will be presented for continuous variables.

# **12.4 Effectiveness Analyses**

# **12.4.1** Analysis of Primary Effectiveness Endpoint(s)

The primary objective of this study is to evaluate the percentage of eyes with BCDVA of 20/20 or better in eyes implanted with AcrySof Toric selected by ORA with VerifEye + and Barrett Toric Calculator. The primary endpoint is percentage of eyes with BCDVA of 20/20 or better at 6 months.

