## 8.1 **Inclusion Criteria**

Written informed consent must be obtained before any study specific assessment is performed. Upon signing informed consent, the subject is considered enrolled in the study.

Subjects eligible for inclusion in this study must fulfill **all** of the following criteria:

- 1. Subject must be able to understand and sign an IRB/IEC approved Informed Consent form.
- 2. Willing and able to attend all scheduled study visits as required per protocol.
- 3. 22 years of age or older
- 4 Preoperative keratometric astigmatism of 0.75 to 3.00 D
- 5. Planned implantation of AcrySof IQ Toric SN6AT3 - T6 as determined by the Alcon **Toric Calculator**
- 6. Potential postoperative visual acuity of 0.04 logMAR (20/20) or better

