## 8.2 **Exclusion** Criteria

Subjects fulfilling **any** of the following criteria are not eligible for participation in this study.

- 1. Pregnancy:
  - they are currently pregnant, a.
  - b. have a positive urine pregnancy test result at Screening,
  - intend to become pregnant during the study period, C.
  - d. are breast-feeding.

Subjects who become pregnant during the study will not be discontinued; however, data will be excluded from the effectiveness analyses because pregnancy can alter refraction and visual acuity results.

2. Unclear intraocular media other than cataract

- 3. Axial length < 21.5 and > 27.0 mm
- 4. Significant irregular corneal astigmatism as measured by a corneal topographer
- 5. Unstable tear film per Investigator judgement
- 6. Significant anterior or posterior segment disease
- 7. Prior intraocular or corneal surgery
- 8. Prior retinal detachment
- 9. Participation in another concurrent clinical trial per the PI judgement
- 10. Presence or history of any condition or finding that makes the subject unsuitable as a candidate for cataract surgery or study participation or may confound the outcome of the study, in the opinion of the Investigator

Exclusion Criteria during Surgery

- 11. Intra-operative complications such as, but not limited to, posterior capsular tear, wound burn and need to place a suture
- 12. ORA or Alcon Toric Calculator recommends an IOL other than AcrySof IQ Toric SN6AT3-T6

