# **10.3 Study Visit Procedures**

# 10.3.1 Visit 0: Day -30 to Day 0 (for both eyes)

Upon signing informed consent, patients are considered enrolled. Subjects will be assigned a single subject identifier at the screening visit. The subject identifier consists of a combination of a 4 digit Investigator number and a 5 digit subject number. The number is automatically generated sequentially by the electronic data capture (EDC) system. As an example: "4584.00001" (the Investigator number and subject number are separated by a "." character).

Below is a list of study procedures to be undertaken at Visit 0. Procedures should be performed in the order presented below unless otherwise stated. All assessments must be documented in the source documentation and eCRFs (if applicable).

For a potential subject meeting all entry criteria via pre-screening, invite him/her to participate in the study, and carry out the informed consent process if he/she is interested.

NOTE: Subjects must formally consent to participate in the study prior to undergoing any study specific testing.

- •
- Document demographics, ocular and nonocular medical history, ocular and nonocular concomitant medications.
- Perform a urine pregnancy test, if the subject is a woman of childbearing potential.

٠	
•	Measure and record BCDVA measurement (monocular) - (refer to MOP for details).
•	
•	Identify target refraction.

• Record any device deficiency and AEs.

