# 12.8 Sample Size Justification

In order to estimate the percent of eyes with BCDVA of 20/20 or better (ie,  $\leq 0.04 \log$ MAR) at 6 months post-operative, the 95% confidence interval of the percent of eyes with BCDVA of 20/20 or better at 6 months post-operative will be calculated based on the binomial distribution. With a sample size of 90 eyes, per the binomial distribution, the width of the 95% confidence interval ranges from 4.0% to 21.5%. As an example, for an observed outcome of 70%, the 95% confidence interval per binomial distribution is (59.4%, 79.2%) with a width of 19.8%.

For different number of available eyes at 6 months (70, 75, 80, 85, 90, 95, and 100) and different observed percent of eyes with BCDVA of 20/20 or better at 6 months (70%, 75%, and 80%), the table below summarizes the corresponding confidence intervals and the width of the confidence intervals. With a sample size of at least 70 eyes at 6 months postoperatively, the width of confidence interval is less than 23% if the observed rate is  $\geq$  70%.

Number of Eyes	Observed Percent of Eyes with BCDVA of 20/20 or Better		
at 6 Months	70%	75%	80%
70	(57.9%, 80.4%)	(64.0%, 85.2%)	(68.7%, 88.6%)
	22.5%	21.2%	19.9%
75	(59.0%, 80.6%)	(63.3%, 84.0%)	(69.2%, 88.4%)
	21.6%	20.7%	19.2%
80	(58.7%, 79.7%)	(64.1%, 84.0%)	(69.6%, 88.1%)
	21.0%	19.9%	18.6%
85	(59.7%, 80.0%)	(64.7%, 84.0%)	(69.9%, 87.9%)
	20.3%	19.3%	18.0%
90	(59.4%, 79.2%)	(65.4%, 84.0%)	(70.2%, 87.7%)
	19.8%	18.6%	17.4%
95	(60.3%, 79.4%)	(64.8%, 83.1%)	(70.5%, 87.5%)
	19.2%	18.3%	17.0%
100	(60.0%, 78.8%)	(65.3%, 83.1%)	(70.8%, 87.3%)
	18.7%	17.8%	16.5%

Table 12-1	95% Confidence Interval and Width per Binomial Distribution
	75 76 Confidence Inter var and Width per Dinomiar Distribution

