2.3 Pharmacokinetic Analysis Set

Not Applicable.

3 Subject Characteristics and Study Conduct Summaries

Subject characteristics and study conduct summaries include tables and listings such as a subject disposition table, demographics and baseline characteristics tables (including age, gender, race, ethnicity), listing of treatment assignments by site, and a summary of screen failures by reason. All descriptive summary statistics will be displayed with n and % for categorical data, and with mean, median, standard deviation, number of subjects, minimum and maximum for continuous data. Tables will be presented by treatment. Subject characteristics and study conduct summaries will be presented for the AAS and the safety analysis set.

4 Effectiveness Analysis Strategy

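### Does using the same 20/20 cut for inclusion criterion 6 and for the primary endpoint call for a change to the plan?

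*Protocol*

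**What the plan says.** The endpoint sentence in Protocol 12.4.1 is "The primary endpoint is percentage of eyes with BCDVA of 20/20 or better at 6 months". SAP 4.1 agrees, and Protocol 12.4.1.2 and SAP 4.3.1.1 score it as 0.04 logMAR or better. (Protocol Table 6-1 lists mean BCDVA against the same objective; that mismatch is a separate matter.)

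Inclusion criterion 6 in Protocol 8.1 is "Potential postoperative visual acuity of 0.04 logMAR (20/20) or better". Protocol 8.2 excludes several other reasons for missing 20/20, among them "Significant irregular corneal astigmatism as measured by a corneal topographer", unstable tear film, significant anterior or posterior segment disease, and, during surgery, "Intra-operative complications such as, but not limited to, posterior capsular tear, wound burn and need to place a suture".

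The arms differ in how the lens and its axis are chosen and how the axis is aligned. In the Barrett group "the IOL power and axis will be provided by the Barrett Toric Calculator and axis alignment will be done manually"; in the ORA group all three come from ORA (Protocol 7.1).

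Protocol 12.8 and SAP 8 give exact binomial intervals for 70 to 100 eyes at observed rates of 70%, 75% and 80%, and a width range of 4.0% to 21.5% at 90 eyes. Protocol 12.4.1.1 plans no hypothesis test, and the SAP executive summary marks the success criterion as not applicable.

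**The concern.** A subject enters only if judged able to reach 0.04 logMAR, and the eye is then scored on whether it reached 0.04 logMAR. The scoring follows best correction, which largely removes the residual sphere and regular cylinder that lens power, axis and alignment act on. Much of what could still keep an eye below 20/20 is excluded.

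If the entry judgment is usually right, both arms would sit near 100% whichever method chooses lenses better, and a reader could take two similar high percentages as evidence that ORA and Barrett perform alike. The figure would also run higher than in toric candidates not selected on visual potential.

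The sample-size section seems to pull the other way. At 70% to 80%, between 0.20 × 90 = 18 and 0.30 × 90 = 27 eyes per arm would miss an acuity they were admitted as able to reach, and neither document says why.

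**Working it through.** **1. The two cuts.** Criterion 6 and the endpoint both use 0.04 logMAR (20/20). Criterion 6 concerns potential acuity, judged before surgery; the endpoint is measured acuity at 6 months. The documents give no rate at which that judgment proves right, and no BCDVA rate with or without the criterion. The size of any ceiling can therefore only be shown over an assumed range.

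**2. The plan's own figures.** The exact (Clopper-Pearson) 95% limits for x of n eyes are

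- lower = 2.5% quantile of Beta(x, n − x + 1)
- upper = 97.5% quantile of Beta(x + 1, n − x)

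For 63/90 (70%) this gives 59.4% to 79.2%, width 19.8, as printed. All 21 cells of Table 12-1 reproduce to 0.1 point, taking the count as a whole number near n × rate. Over every possible count at n = 90, the width runs from 4.02 (0/90 or 90/90) to 21.46 points, which is the stated 4.0% to 21.5%. At n = 70 with an observed rate of at least 70%, the largest width is 22.51, below the stated 23%.

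**3. Precision nearer the ceiling.** Assume 90% to 100% of eyes reach 20/20 (n = 90 per arm; widths come from unrounded limits):

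| Eyes at 20/20 | Rate | Exact 95% CI | Width |
|---|---|---|---|
| 63/90 | 70.0% | 59.4 to 79.2 | 19.8 |
| 81/90 | 90.0% | 81.9 to 95.3 | 13.5 |
| 86/90 | 95.6% | 89.0 to 98.8 | 9.8 |
| 90/90 | 100% | 96.0 to 100 | 4.0 |

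Higher rates give narrower intervals, all inside the range the plan states. The 4.0% end of that range is the 90/90 result, so the plan already covers the ceiling.

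**4. Room to differ.** Suppose the other arm is perfect at 90/90 and k of 90 subjects are discordant, all in its favor. The gap is k/90 and the paired Wald 95% half-width is 1.96 × √(k − k²/90) / 90:

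| Lower arm | k | Largest gap | Half-width |
|---|---|---|---|
| 63/90 | 27 | 30.0 points | 9.5 points |
| 81/90 | 9 | 10.0 points | 6.2 points |
| 87/90 | 3 | 3.3 points | 3.7 points |

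At 87/90 even a perfect comparator gives a gap smaller than its own half-width. The insensitivity is real if rates are that high.

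**5. What a change could add.** With endpoint, eligibility and sample size kept, the candidates are these:

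- *A caption on the primary table.* The restriction is already stated in the eligibility criteria, and the endpoint's name says it is best corrected.
- *The percentage at 0.00 logMAR or better and the mean logMAR shown beside it.* SAP 4.3.1.1 already plans both by treatment. Both use the same selected eyes and the same corrected measurement, so they share the limitation.
- *A count of subjects failing criterion 6.* SAP 3 already plans "a summary of screen failures by reason". The count would be incomplete in any case, because Protocol 10.3.1 says "For a potential subject meeting all entry criteria via pre-screening, invite him/her to participate in the study", so some exclusions happen before consent.
- *Extra columns at 90% to 100% in the SAP 8 table.* The stated width range covers them, and changing one table would make it differ from its twin in Protocol 12.8.

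None of these alters a percentage, an interval or a decision.

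**The case for a change.** The best argument for acting is that, with no test and no success criterion, the displayed percentage is the study's main product, so its meaning matters more than usual. The protocol's introduction frames the clinical problem as residual refractive error and uncorrected acuity, and Section 5.3.2 names unexpected postoperative refraction as the calculator's key harm. A best-corrected measure sits at some distance from both. A label would cost only an SAP amendment.

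Part of this stands: the endpoint is a weak instrument for separating the two methods, and it describes eyes selected for good visual potential. The rest does not carry through.

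- The stated purpose (Protocol 5.2) is to evaluate visual acuity outcomes with both technologies, and BCDVA is such an outcome. The same section assigns the effectiveness of each device to exploratory measurements. Their list is not visible in the public text, so refractive outcomes cannot be called absent.
- The 70-80% rates are not forecasts. Section 12.8 offers 70% as an example and labels all three as observed percentages. Nothing says they are expected or that they set the sample size, so there is nothing to reconcile with criterion 6.
- That the percentages mainly reflect case selection is a reasonable inference, but it cannot be shown. If the observed rates do fall at 70% to 80%, 20 to 30 points of room remain.
- Criterion 6 is confirmed at Visit 0 before randomization (Protocol 9.3.1) and each subject contributes an eye to each method, so it does not bias the comparison. This reasoning covers criterion 6 only. The exclusions during surgery come after randomization and raise a different question.

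**Conclusion.** No change to the plan. The shared cut and the best-corrected scoring are a fair trade-off: eyes with poor visual potential are kept out of a descriptive acuity study, at the cost of sensitivity to refractive differences. Followed as written, the plan yields correct percentages and correct exact intervals. Per-arm precision at 90 eyes is 4.0 to 13.5 points at assumed rates of 90% to 100%, better than the 17.4 to 19.8 points tabulated for 70% to 80%. What shrinks is the possible gap between arms, to 10 points or fewer at 90% and above, and nothing in the plan is decided on that gap.

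The 90% to 100% range is an assumption, since the documents give no rate, and the conclusion does not depend on where in it the truth lies. It rests on the analysis staying descriptive by arm. A report writer would ordinarily say that the percentage applies to eyes judged able to reach 20/20 and scored after correction. If the two percentages come out high and alike, they should not be read as showing that the methods are equally accurate in refraction.
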